13.3.3 Whole Blood to Plasma Partitioning Ratio

The percentage of TRA in whole blood relative to plasma (i.e., whole blood:plasma partitioning ratio) will be estimated at each time-matched determination of TRA in whole blood and plasma collected at the scheduled time points as delineated in the Study Events Flow Chart ([Section 6](#)).

13.3.4 Urine Sampling and Processing

Urine for determination of TRA and metabolite profiling will be collected at the specified intervals delineated in the Study Events Flow Chart ([Section 6](#)).

Prior to the predose sample collection, each subject will be instructed as to urine collection methods. All urine during an interval is to be collected.

On Day 1, a spot collection will be obtained prior to dosing for the predose sample. Subjects will be asked again to empty their bladder within approximately 15 minutes prior to dosing, and no urine will be collected at this time unless it is needed for the predose sample. Only one predose urine sample will be collected on Day 1.

Subjects will be encouraged to void at the end of each collection interval. If they do void at any time during the collection interval, the time should be documented. Should this be the case, subjects need to void again at the end of the collection period, as scheduled. However, should subjects be unable to void, this will be documented as well.

Urine will be refrigerated during the collection intervals. At the end of each interval, urine will be pooled and thoroughly mixed. Total urine volume will be weighed and recorded.

Predose samples should be handled, processed, analyzed, and stored separately away from the postdose samples to avoid cross contamination.

Instructions for urine sampling, collection, processing, and sample shipment will be provided separately.

13.3.5 Urine Pharmacokinetic Parameters

PK parameters for urine TRA will be calculated as follows:

Ae(u):	Amount of TRA excreted in urine within a given collection interval.
CumAe(u):	Cumulative amount of TRA excreted in urine.
%Dose(u):	Percent of administered radioactive dose excreted in urine within a given collection interval.
Cum%Dose(u):	Cumulative percent of administered radioactive dose recovered in urine.
CLr:	Renal clearance. CLr = CumAe(u)/AUC0-inf, where both CumAe and AUC are determined over matched time interval.

13.3.6 Fecal Sampling and Processing

Fecal samples for the determination of TRA and metabolite profiling will be collected at the specified intervals delineated in the Study Events Flow Chart ([Section 6](#)).

The predose fecal sample is to be obtained within 48 hours prior to dosing. Subjects will be asked to bring a fecal sample at Check-in (if produced within 48 hours prior to dosing). Feces produced between Check-in and dosing will also be collected as a predose sample with the sample produced nearest to dosing to be retained as the only predose sample.

All fecal samples will be collected and stored individually for analysis of TRA and for metabolite profiling. The samples will be weighed at the time of collection. Multiple fecal samples from a given subject in a given interval will be pooled into a single sample at the time of homogenization.

Predose samples should be handled, processed, analyzed, and stored separately away from the postdose samples to avoid cross contamination.

Instructions for fecal sampling, collection, processing, and sample shipment will be provided separately.

13.3.7 Fecal Pharmacokinetic Parameters

PK parameters for feces TRA will be calculated as follows:

Ae(f):	Amount of TRA excreted in feces within a given collection interval.
CumAe(f):	Cumulative amount of TRA excreted in feces.

%Dose(f): Percent of administered radioactive dose excreted in feces within a given collection interval.

Cum%Dose(f): Cumulative percent of administered radioactive dose recovered in feces.

13.3.8 Emesis

Collection containers (pre-weighed) for emesis will be available for subjects participating in the study at all times following dosing until discharge from the clinic. Subjects will be instructed at the beginning of the study that they should use one of the designated containers if emesis occurs following [¹⁴C]-CT1812 dosing. If emesis occurs following [¹⁴C]-CT1812 dosing and the subject has been able to collect the emesis in the designated container, it will be weighed and recorded, labeled with subject identification, time, and date, and analyzed for TRA. The subject may continue the study with permission from the Sponsor; however, subject data will be excluded from the PK or mass balance calculations if the AE of vomiting occurs at or before 2 times the median Tmax.

13.3.9 Future Research

No additional analysis is planned to be performed on the PK blood/urine samples for possible future research. Any additional research on these samples unspecified by this protocol will require approval from the subjects.

13.3.10 Analytical Method

Samples from all subjects will be assayed even if the subjects do not complete the study.

Plasma concentrations of CT1812 and metabolite M6 will be determined using validated analytical methods. Whole blood, plasma, urine, and feces TRA will be determined with liquid scintillation counting or AMS detection. Profiling and identification of metabolites in plasma, urine, and where possible, feces will be conducted using standard laboratory procedures. Specifics of the analytical methods will be provided in separate documents.

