5 SYNOPSIS

Compound:	CT1812
Clinical Indication:	Alzheimer's Disease (AD) dementia or prodromal mild cognitive impairment (MCI) due to AD
Study Phase and Type:	Phase 1 – absorption, metabolism, excretion, and mass balance study
Study Objectives:	
Primary objectives:
 
• To determine the route(s) of elimination and the overall mass balance of CT1812 following a single oral dose of [¹⁴C]-CT1812 administered in healthy adult male subjects.• To quantitate total radioactivity (TRA) concentration equivalents in whole blood, plasma, urine, and feces following a single oral dose of [¹⁴C]-CT1812 administered in healthy adult male subjects.• To characterize the PK profile of CT1812 and its metabolite, M6, in plasma following a single oral dose of [¹⁴C]-CT1812 administered in healthy adult male subjects.• To characterize the metabolite profile of CT1812 in plasma, urine, and feces following a single oral dose of [¹⁴C]-CT1812 in healthy adult male subjects and identify the chemical identity of each metabolite accounting for more than 10% of circulating TRA. 
Secondary objectives:
 
• [REDACTED]• [REDACTED]• [REDACTED]
Summary of Study Design:	
This is an open-label, single-dose study to assess the absorption, metabolism, excretion, and mass balance for [¹⁴C]-CT1812.
 
Subjects will be admitted to the [REDACTED] on Day -1 and discharged from the [REDACTED] following completion of 168 hours postdose procedures (Day 8).
 
On Day 1, subjects will receive a single oral dose of 300 mg CT1812 (2 capsules) with a microtracer dose of ~1 μCi [¹⁴C]-CT1812 (1 capsule). Whole blood, plasma, urine, and fecal samples will be

CONFIDENTIAL

CT1812, CA35306, Final Protocol, Amendment 1_15Dec2021

	
collected over 168 hours postdose (Day 8) to measure total radioactivity (all samples), CT1812 and M6 metabolite concentrations (plasma), and for metabolite profiling and identification (plasma, urine, and fecal samples).
 
[REDACTED] will attempt to contact all subjects who received the study drug (including subjects who terminate early) using their standard procedures approximately 14 days after dosing to determine if any adverse event (AE) has occurred since the last visit.

Number of Subjects:	Eight (8), healthy, adult male subjects will be enrolled.

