In the MAD part, each cohort consisted of 8 subjects who received CT1812 and 2 subjects who received matching placebo once daily (QD) for up to 14 days. Following multiple-dose administration (280 mg and 560 mg [younger cohorts] and 560 mg [older cohort]), PK profiling was performed on samples drawn from participants on Day 3 and Day 14 of dosing. Tmax ranged from 0.5 to 4.0 hours with the median Tmax for each cohort ranging from 0.88 to 2.0 hours. The t_{1/2} ranged from 8.93 to 12.3 hours with no linear correlation with dose. Individual t_{1/2} ranged from 6.14 to 21.7 hours. Plasma exposure (AUC₀₋₂₄) and Cmax were approximately dose-proportional and showed modest accumulation compared to QD dosing in the SAD part. The healthy elderly subjects dosed with 560 mg of CT1812 for 14 days demonstrated mean plasma concentrations of CT1812 between that of the 560 mg and the 840 mg doses in healthy young subjects. Mean Cmax was 31% above, Tmax similar, and AUC₀₋₂₄ was 58% above the 560 mg dose parameters in normal healthy young subjects. Cerebrospinal fluid (CSF) was drawn from participants in the 560 mg and 840 mg cohorts 23 hours after dosing on Days 7, 8, or 9 for determination of CT1812 concentrations. Subjects dosed with 560 mg had a mean (\pm standard deviation) CSF concentration of 8.01 (4.26) ng/mL. Subjects in the 840 mg cohort had a mean CSF concentration of 23.3 ng/mL. These results indicate CNS penetration of CT1812 following oral dosing. Multiple dose exposure of CT1812 corresponded to more than 20 times the expected minimum therapeutic dose (34 to 38 mg) while CSF analysis indicated that brain concentrations exceeded the minimum target expected to improve memory (>80% receptor occupancy).

Following CT1812 (90, 280, and 560 mg) administered QD to patients with mild to moderate AD for 28 days, preliminary PK analysis showed evidence of modest accumulation of CT1812 as indicated by plasma AUC values. Both AUC₀₋₂₄ and Cmax estimates were higher on Day 28 than on Day 1, and pre-dose trough concentrations increased across the

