8.2 Rationale

8.2.1 Rationale for this Study and Study Design

The disposition of any drug in the body is controlled by physiological processes affecting absorption, metabolism, and excretion. The most efficient and well-established approach to elucidate these processes is a mass balance study in which the drug dose is administered in radiolabeled form, followed by collection and analysis of different biological matrices for radioactivity using liquid scintillation count and determination of drug concentration using conventional liquid chromatography-tandem mass spectrometry and metabolite profile using liquid chromatography with radiometric detection. The PK, metabolic pathways, and routes of elimination of CT1812 have been evaluated in vitro and in vivo in preclinical species (IB, Version 5.0). In this study the TRA of [¹⁴C]-CT1812 will be measured using accelerator mass spectrometry (AMS).

Additionally, the PK profile of CT1812 in humans has been evaluated in healthy subjects (in a SAD and MAD investigation [Study COG0101]). Currently, the biotransformation/metabolism and excretory pathways of CT1812 in humans are not known.

The aim of this study is to characterize the plasma exposure, clearance pathways, and excretion routes for CT1812 and its metabolites in healthy male subjects following oral administration. Based on data in healthy subjects, the average t_{1/2} of CT1812 following single oral administration in the fasted state for doses from 10 mg to 1120 mg (Study COG0101) ranged from 11.1 to 14 hours, thus, it is expected that more than 90% of the radioactivity should be eliminated within 168 hours postdose, the sampling duration in this study.

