8.2.2 Rationale for the Dose Selection

The single dose consisting of 300 mg (~1 μ Ci) [¹⁴C]-CT1812 oral capsules chosen for this study is expected to provide sufficient mass of drug, and sufficient specific radioactivity (using AMS analysis), for detection and analysis of parent drug and/or metabolites in whole blood, plasma, urine, and fecal samples, as applicable, with CT1812 exposures that are in a safe and pharmacologically active range. Single doses of CT1812 (10 mg – 1120 mg), administered previously to healthy subjects appeared to be safe and well tolerated with the majority of events reported being mild in severity.

The effective dose of radiation for a human male following a single oral administration of 1 μ Ci of [¹⁴C]-CT1812, was calculated to be 0.036 mrem. The effective dose is <20 x than what the average American receives in one day from natural background radiation (NCRP, 2009). Estimated radiation doses from a 1 μ Ci oral administration of [¹⁴C]-CT1812 are below the radiation dose limits set forth in 21 Code of Federal Regulations (CFR) 361 for the whole body, active blood-forming organs, lens of the eye, gonads, and any other organ. The extrapolated 0.036 mrem effective dose represents 0.0012% of the FDA limit (3000 mrem to the whole body, active blood-forming organs, lens of the eye, or gonads). Based on these results, a dose of 1 μ Ci of [¹⁴C]-CT1812 can be administered to a human and be recognized as safe under FDA guidelines (CFR Title 21, 2019).

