13.4 Blood Volume Drawn for Study Assessments

Table 1: Blood Volume during the Study

Sample Type	Number of Time Points	Approximate Volume per Time Point * (mL)	Approximate Volume per Aliquot (mL)	Approximate Sample Volume Over Course of Study (mL)
Screening laboratory safety tests (including hematology, serum chemistry, and serology)	1	12.5	-	12.5
On-study hematology and serum chemistry	3	12.5	-	37.5
Blood for plasma CT-1812 and M6 PK	18	6	2 mL (1 mL primary +1 mL backup)	108
Blood for plasma TRA	18	3	1 mL (0.5 mL primary and 0.5 mL backup)	54
Blood for plasma metabolite profiling and identification	18	10	4 mL (2 mL primary +2 mL backup)	180
Blood for whole blood TRA	18	2	2 mL (1 mL primary 1 mL backup)	36
Total Blood Volume (mL)→				428**

* Represents the largest collection tube that is expected to be used (a smaller tube may be used).

** If additional PK and safety analysis is required to obtain sufficient plasma/serum for analysis, additional blood may be obtained (up to a maximum of 50 mL).

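### Does letting Section 13.3.10 use liquid scintillation counting put the total-radioactivity results at risk at a ~1 µCi dose?

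*Protocol*

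**What the plan says.** Three places in the protocol bear on how total radioactivity (TRA) is measured.

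- Section 8.2.1 first describes the usual mass-balance approach, which uses liquid scintillation counting. It then says that in this study TRA "will be measured using accelerator mass spectrometry (AMS".
- Section 8.2.2 justifies the dose as giving "sufficient specific radioactivity (using AMS analysis), for detection and analysis of parent drug and/or metabolites in whole blood, plasma, urine, and fecal samples". The Synopsis describes the dose as "a single oral dose of 300 mg CT1812 (2 capsules) with a microtracer dose of" about 1 µCi.
- Section 13.3.10, the assay section, reads: "Whole blood, plasma, urine, and feces TRA will be determined with liquid scintillation counting or AMS detection". It gives no allocation by matrix, time point or activity. It closes by leaving the specifics of the methods to separate documents.

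Table 1 in Section 13.4 gives a 0.5 mL primary plasma aliquot for TRA. The document supplied as the SAP is a bioanalytical plan for CT1812 and M6 in plasma and does not deal with TRA. Neither document states a quantification limit for scintillation counting or AMS.

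**The concern.** The assay section appears to allow a method for which the dose was never justified. One µCi is 2.22 million disintegrations per minute (dpm) in the whole body, so a small plasma aliquot contains very little. Much depends on plasma and blood TRA: the TRA exposure parameters, the whole blood to plasma ratio, the ratio of CT1812 to TRA, and the criterion that a metabolite exceed 10% of circulating radioactivity. Under Section 13.3.2, AUC0-t ends at the last time when plasma TRA and CT1812 are quantifiable in all subjects, so one subject with a poor detection limit would shorten it for everyone.

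Excreta raise a similar worry. If low-activity intervals fell below a counting limit and were dropped, summed recovery and the split between urine and feces would be biased. Both belong to the first primary objective. A quick bound multiplies the daily amount that can hide below the limit by seven days. That gives 6 to 19% of dose, which would be serious against an expected elimination of over 90%.

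**Working it through.** **Inputs from the protocol.** About 1 µCi with 300 mg; 0.5 mL plasma aliquot; urine intervals 0–4, 4–8, 8–12 and 12–24 h, then every 24 h to 168 h; average single-dose half-life that "ranged from 11.1 to 14 hours"; individual multiple-dose half-lives that "ranged from 6.14 to 21.7 hours".

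**Assumptions not in the documents.** Distribution volume 30 to 300 L; urine 2 L/day; feces 150 g/day; mono-exponential excretion at the parent half-life; counting background 10 to 30 cpm, efficiency 90%, counting time 5 to 60 min.

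**The plan's own figures.**
- Radiation dose: 0.036/3000 × 100 = 0.0012%, as stated.
- Remaining at 168 h: 2^(−168/11.1) = 0.003% and 2^(−168/14) = 0.024%. The expectation of over 90% elimination follows.

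**What a counter can quantify.** The Currie limit at 10% precision is 50 × [1 + √(1 + BT/12.5)]/(0.9 × T), where B is background in cpm and T is minutes.
- B = 10, T = 60: 50 × (1 + 7)/54 = 7.4 dpm per vial.
- B = 30, T = 5: 50 × (1 + 3.606)/4.5 = 51 dpm per vial.

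**Plasma.** dpm per 0.5 mL = 0.5 × 2.22×10⁶/(V × 1000) × 2^(−t/12.5), with the whole dose placed in volume V at time 0.

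| V (L) | 0 h | 24 h | 48 h |
|---|---|---|---|
| 30 | 37 | 9.8 | 2.6 |
| 100 | 11 | 2.9 | 0.8 |
| 300 | 3.7 | 1.0 | 0.3 |

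Even at an extreme 3 L and a 14 h half-life, the aliquot falls from 370 dpm to 10.5 dpm at 72 h and 0.09 dpm at 168 h. Scintillation counting could not support the full plasma profile.

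**Early excreta.** At a 14 h half-life, 69.5% of the dose leaves in the first 24 h, or 1.54×10⁶ dpm. If 10% is renal, urine holds 1.54×10⁶ × 0.1/2000 = 77 dpm/mL. If all is fecal, feces hold 1.54×10⁶/150 ≈ 10,300 dpm/g. Both can be counted.

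**Most that could be missed in urine.** An assumed limit of L dpm/mL hides at most L × 2000/2.22×10⁶ of the dose per 24 h: 0.90% at L = 10 and 2.70% at L = 30. Seven times these is 6.3% and 18.9%, but that requires urine to sit just below the limit every day without declining. Under mono-exponential excretion, each day's amount is r = 2^(−24/t½) times the previous day's. Once one day is just below the limit, the total missed from then on is the daily limit × (1 + r + r² + …), which is at most the daily limit/(1 − r).

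| t½ (h) | r | L = 10 | L = 30 |
|---|---|---|---|
| 11.1 | 0.223 | 0.90/0.777 = 1.2% | 2.70/0.777 = 3.5% |
| 12.5 | 0.264 | 0.90/0.736 = 1.2% | 2.70/0.736 = 3.7% |
| 14 | 0.305 | 0.90/0.695 = 1.3% | 2.70/0.695 = 3.9% |

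A search over renal fractions up to 100%, using the protocol's actual urine intervals, gives the same maxima. The shorter first-day intervals do not raise them. At 21.7 h the range is 1.7 to 5.0%. At an assumed 48 h it is 2.7 to 8.1%.

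**Feces.** Counting 0.5 g with a limit of 10 to 30 dpm per vial hides at most 0.135 to 0.405% of dose per day. At 14 h the total is 0.135/0.695 = 0.2% to 0.405/0.695 = 0.6%.

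**The case for a change.** The strongest argument for a change is that the sections do not say the same thing. Read alone, Section 13.3.10 permits scintillation counting for every sample, plasma included, and documents held elsewhere do not remove a mismatch within the protocol. If a laboratory did count plasma, the TRA profile would be cut short and AUC0-t with it. A minor urinary route could also go unseen in every interval. At 14 h and 10 to 30 dpm/mL, the 0–4 h limit is L × 333/2.22×10⁶ = 0.15 to 0.45% of dose, and 18.0% of renal excretion falls in that interval, so a route of up to about 0.8 to 2.5% of dose could be missed entirely.

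The mismatch is real, and the plasma arithmetic holds across every volume examined. But the harm requires the laboratory to set aside the explicit commitment in Section 8.2.1 and the dose rationale in Section 8.2.2. The two methods joined by 'or' can be read coherently as AMS where activity is low and counting where it is ample, and early excreta are ample. The documents nowhere say that a below-limit result enters the sums as zero. Nor do they establish that the dose is too small for counting in general: that depends on assumed limits and volumes, and late feces could be counted if radioactivity cleared more slowly than parent drug (about 540 dpm/g at 144–168 h with an assumed 48 h half-life and all-fecal excretion).

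**Conclusion.** No change to the plan follows. Section 13.3.10 is worded more loosely than Sections 8.2.1 and 8.2.2, but AMS satisfies all three and nothing obliges anyone to use scintillation counting where it would fail. What is missing is an allocation rule. Section 13.3.10 leaves such detail to separate documents that are not among those supplied, and a laboratory running a ~1 µCi microtracer study would fill the gap sensibly.

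The size supports this. For plasma, counting is so plainly inadequate over 168 h that it is not a realistic choice. For excreta, the worst case at half-lives of 11.1 to 14 h is about 1.2 to 3.9% of dose in urine and at most 0.6% in feces, together no more than 4.5%. These bounds rest on assumed counting limits, daily output and mono-exponential excretion at the parent half-life. Slower clearance of radioactivity would raise the urine bound, to about 8% at an assumed 48 h. They also require that excreta be counted and below-limit intervals ignored, which the plan does not prescribe.

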13.4 Blood Volume Drawn for Study Assessments

Table 1: Blood Volume during the Study

Sample Type	Number of Time Points	Approximate Volume per Time Point * (mL)	Approximate Volume per Aliquot (mL)	Approximate Sample Volume Over Course of Study (mL)
Screening laboratory safety tests (including hematology, serum chemistry, and serology)	1	12.5	-	12.5
On-study hematology and serum chemistry	3	12.5	-	37.5
Blood for plasma CT-1812 and M6 PK	18	6	2 mL (1 mL primary +1 mL backup)	108
Blood for plasma TRA	18	3	1 mL (0.5 mL primary and 0.5 mL backup)	54
Blood for plasma metabolite profiling and identification	18	10	4 mL (2 mL primary +2 mL backup)	180
Blood for whole blood TRA	18	2	2 mL (1 mL primary 1 mL backup)	36
Total Blood Volume (mL)→				428**

* Represents the largest collection tube that is expected to be used (a smaller tube may be used).

** If additional PK and safety analysis is required to obtain sufficient plasma/serum for analysis, additional blood may be obtained (up to a maximum of 50 mL).

14 STATISTICAL CONSIDERATIONS

Data will be handled and processed according to Celerion Standard Operating Procedures, which are written based on the principles of GCP.

14.1 Sample Size Determination

The sample size of 8 healthy male subjects was selected without statistical considerations and in order to have complete data from 6 subjects available for evaluation. It has been determined adequate to meet the study objectives. This sample size is limited based on clinical considerations for this type of study and in order to limit exposure to radioactivity.

14.2 Population for Analyses

PK Population: All subjects who comply sufficiently with the protocol and display an evaluable PK profile (e.g., exposure to treatment, availability of measurements and absence of major protocol violations or an AE of vomiting as described) will be included in the statistical analysis.

Safety Population: All subjects who received the dose of the study drug will be included in the safety analysis.

14.3 Statistical Analyses

Detailed methodology for summary and statistical analyses of the data collected in this study will be documented in a Statistical Analysis Plan (SAP). The SAP will be prepared by Celerion and agreed upon with the Sponsor. This document may modify the plans outlined in the protocol; however, any major modifications of the primary endpoints definition and/or its analysis will also be reflected in a protocol amendment. Additional statistical analyses other than those described in this section may be performed if deemed appropriate.

